5.4 Exclusion criteria

- Have or have had hepatitis C with a proven cure by viral load at 12 weeks after the end of treatment without risk behaviors for reinfection.
- Be on antiviral treatment against chronic hepatitis C virus.
- That the patient voluntarily and consciously refuses to sign the informed consent form or is unable to give it due to any type of physical and/or mental disability.

5.5 Variables

Table 1. Study variables

Category	Variable name	Conceptual definition	Operational definition	Measuring scale
Sociodemographic	ID Number	ID Number	Personal identification number under which you are registered in the country of origin	Nominal
	Age	Duration of an individual's existence measured in units of time.	Number in years	Continual
	Gender	Categorizes the	1. Female	Nominal

Category	Variable name	Conceptual definition	Operational definition	Measuring scale
		individual according to her biological characteristics.	0. Male 2. Undetermined	
	Nationality	Country of birth	Name of country	Nominal
	Department of Residence	A geographic place to which the municipality or city where the person usually resides belongs.	Name of department	Nominal
	Municipality of residence	Geographic place municipality/city where the person usually resides.	Name of municipality/city	Nominal
	Health Service Provider Institution (IPS)	Place where the screening was performed.	1= Fundación cardioinfantil 2= Fundación Santafé 3= Clínica Colombia 4= Hospital Universitario San Ignacio 5= Fundación Valle de Lili 6= Hospital Pablo Tobón Uribe 7= Hospital Universitario Julio Méndez Barreneche E.S.E.	Nominal, polytomous
	Affiliation regime	Category of affiliation to the health system.	0=Not insured 1=Subsidized 2=Contributory 3=Special 4=Exception	Nominal, polytomous
	Entity Benefit plan administrator (EAPB) or Entity obliged to compensate (EOC)	The entity in charge of health care coverage.	Name of entity	Nominal
Risk Factors	Transfusion of blood products	Administration of hemocomponents before 1996.	0. No 1. Yes	Nominal, dichotomous

Category	Variable name	Conceptual definition	Operational definition	Measuring scale
	The year in which you received the transfusion	Date (year) in which you received the transfusion.	The year in which you received the transfusion	Continual
	Major surgery	Surgical procedure performed in the operating room under general or regional sedation that may require post-procedural in-hospital monitoring.	Abdominal laparotomy: 0. no; 1 Yes Gynecologic surgery of any type: 0. No; 1 Yes Orthopedic surgery of any type: 0. No; 1 Yes Any surgery that required in-hospital post-procedure surveillance for more than 24 hours: 0. 0. No; 1 Yes	Nominal, dichotomous
	Intravenous drug use	Having consumed intravenous drugs at any time.	0. No 1. Yes	Nominal, dichotomous
	Inhaled or intranasal drug use	Having consumed inhaled drugs at any time.	0. No 1. Yes	Nominal, dichotomous
	Men who have sex with men	Man who has had sex with men.	0. No 1. Yes	Nominal, dichotomous
	Known hepatitis B virus infection	Refer to have a diagnosis of hepatitis B virus.	0. No 1. Yes	Nominal, dichotomous
	Known HIV infection	Refer to HIV diagnosis.	0. No 1. Yes	Nominal, dichotomous
	People who have had tattoos, body piercings, scarification, etc.	Presence of tattoos or piercing or scarification.	0. No 1. Yes	Nominal, dichotomous
	Population deprived of liberty or previously incarcerated persons	Being or having been deprived of liberty in a penitentiary center.	0. No 1. Yes	Nominal, dichotomous
	Liver disorders or disease	A person with abnormal liver	0. No 1. Yes	Nominal, dichotomous

Category	Variable name	Conceptual definition	Operational definition	Measuring scale
		tests or liver disease.		
	Occupational exposure	Healthcare workers or members of public safety (e.g., correctional service officers or police) who have been in contact with blood at work through needlestick or sharps injuries.	0. No 1. Yes	Nominal, dichotomous
	Hemodialysis	A person who has undergone hemodialysis.	0. No 1. Yes	Nominal, dichotomous
	Comorbidities potentially associated with HCV infection.	Diabetes, Ischemic heart disease, Cryoglobulinemia, Chronic renal failure, Sjögren's syndrome, Hypothyroidism, Flat lichen, Rheumatoid arthritis, Non-Hodgkin's lymphoma, Acute lymphoblastic leukemia, Waldenstrom's macroglobulinemia, Chronic renal insufficiency, Sjögren's syndrome	0. No 1. Yes	Nominal, dichotomous
Missed opportunity	Doctor visits	Doctor visits in the last month	How many?	Continued
Sample results	HCV antibody screening test	Report of HCV antibody test result.	0. Non-reactive 1. Reactive	Nominal, dichotomous
	Viral load test	Report the viral load result of those patients who presented reactive HCV antibodies.	0. Non-reactive 1. Reactive	Nominal, dichotomous

Category	Variable name	Conceptual definition	Operational definition	Measuring scale
Follow-up	SIVIGILA Report	The confirmed cases of HCV as a public health event are reported to the surveillance system utilizing form 340.	0: Not reported 1: If reported	Nominal, dichotomous
	Follow-up of confirmed case	Follow-up that each case confirmed in the study has access to consultation by a clinical specialist.	0. No Why? 1. Yes	Nominal, dichotomous
		Monitoring patient access to treatment	0. No Why? 1. Yes	Nominal, dichotomous

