5.2 Study population

All persons over 18 years of age who are treated in the included health care institutions (IPS) and who are users of hospitalization, emergency, outpatient and any other hospital care services.

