5.3 Inclusion criteria

Have at least one of the following risk factors for hepatitis C.

- Over 50 years of age with no risk factors.
- Over 18 years old and < 50 years old, with risk factors for hepatitis C:
 - ✓ Persons who have received medical or dental interventions in health care settings.
 - ✓ Persons who have had tattoos, body piercings, or scarification procedures.
 - ✓ Persons with HIV or hepatitis B infection.
 - ✓ Persons who inject drugs.
 - ✓ Persons who have used intranasal drugs.
 - ✓ Persons deprived of liberty and previously incarcerated persons.
 - ✓ Anyone with abnormal liver tests or liver disease.
 - ✓ Students, health care workers, or members of public safety (e.g. correctional

service officers or police) who have come into contact with blood at work through needlestick or sharps injuries.

- ✓ Anyone who has undergone hemodialysis.
- ✓ Persons who received transfusions in Colombia before 1996.
- ✓ Persons with comorbidities potentially associated with CH: diabetes, ischemic heart disease, cryoglobulinemia, chronic renal failure, Sjögren's syndrome, hypothyroidism, lichen planus, rheumatoid arthritis, HIV, non-Hodgkin's lymphoma, acute lymphoblastic leukemia, waldenstrom's macroglobulinemia.
- Individuals previously treated for HCV with sustained viral response in whom reinfection is suspected (individuals who continue to engage in risk behaviors)
- Accept to participate in the study by signing the informed consent form.

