12.1 Annex 1. Data collection instrument

Adult screening for hepatitis C and linkage to treatment in Colombian hospitals	
Patient's name:	Identification number:
Age (in years):	Sex: Male: ___ Female: ___
Contact phone number:	Residence address: Department of Residence: Municipality of residence:
Affiliation scheme: 0. Uninsured: _____ 1. Subsidized: _____ 2. Contributory: _____ 3. Special: _____ 4. Exception: _____	Institución prestadora de servicio de salud (IPS): Fundación cardiointantil _____ Fundación Santafé _____ Clínica Colombia _____ Hospital Universitario San Ignacio _____ Fundación Valle de Lili _____ Hospital Pablo Tobón Uribe _____ Hospital Universitario Julio Méndez Barreneche E.S.E. _____
E-mail: _____ Nationality: _____	
Received blood transfusion before 1996: YES ___ NO ___	Year of transfusion:
Name of EAPB or Entity obliged to compensate:	Major Surgery: Yes ___ No ___ Type of surgery: Abdominal laparotomy: Yes ___ No ___ Gynecologic surgery of any type: Yes ___ No ___ Orthopedic surgery of any type: Yes ___ No ___ Any surgery that has required post-procedure in-hospital surveillance: Yes ___ No ___
Tattoos: Yes ___ No ___	Intravenous drug user: Yes ___ No ___ Nasal drug user: Yes ___ No ___
Man who has sex with men: Yes ___ No ___	Known hepatitis B virus infection: Yes ___ No ___
Known HIV infection: Yes ___ No ___	Have you ever had tattoos or body piercings? Yes ___ No ___
Abnormal liver tests or with liver disease:	Healthcare workers or members of public

Yes__ No__	safety (e.g., correctional service officers or police) who have come into contact with blood at work through needle sticks or sharps injuries: Yes__ No__
A person who has undergone hemodialysis: YES__ NO__	Diagnosis of diabetes: YES__ NO__
Diagnosis of Cryoglobulinemia: YES__ NO__	Diagnosis of coronary artery disease: YES__ NO__
Diagnosis of renal failure: YES__ NO__	
Population deprived of liberty or previously incarcerated persons: YES __NO__	
HCV antibody detection test: Non-reactive: _____ Reactive: _____	
Viral load test: Positive: _____ Negative: _____ Not applicable: _____(in all cases where HCV antibody screening test is non-reactive).	
Case reported to Sivigila YES__ NO__	
The positive case has been followed up YES __NO__	
The patient has had access to a specialized consultation YES __NO__ Why?	
The patient was able to access treatment YES __NO__ Why?	
Date of completion:	
Name of the person doing the diligence:	

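### Major surgery and hemodialysis carry no time anchor in a sample that includes inpatients, so same-stay procedures count as exposure and cannot be separated later; the surgery threshold also differs between Table 1 and Annex 1

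*Combined protocol and SAP*

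**What the plan says.** Section 5.2 defines the population as adult "users of hospitalization, emergency, outpatient and any other hospital care services", and section 5.6 repeats this for the sampling frame. Section 5.9 describes opportunity screening and does not place the test at admission or before any procedure.

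Table 1 in section 5.5 describes major surgery conceptually as an operating-room procedure "that may require post-procedural in-hospital monitoring". It then codes four Yes/No items: laparotomy, gynecologic surgery, orthopedic surgery, and a residual item, "Any surgery that required in-hospital post-procedure surveillance for more than 24 hours". Hemodialysis is coded Yes/No as "A person who has undergone hemodialysis". Neither variable has a date or a look-back window, and neither excludes the present stay.

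Annex 1 collects the same items. The residual surgery item there reads "Any surgery that has required post-procedure in-hospital surveillance", with no duration. Hemodialysis appears as "A person who has undergone hemodialysis: YES__ NO". The only date for the record as a whole is the date the form was completed.

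Transfusion is treated differently. Table 1 limits it to "Administration of hemocomponents before 1996", and both Table 1 and Annex 1 ask for the year.

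Section 4.2 lists an exploratory analysis of risk factors against positive cases. Section 5.10 carries it out with bivariate chi-square tests against positive antibodies.

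**The concern.** A risk factor for an existing infection has to come before it. A patient screened after an operation, or after a first dialysis session, in the current stay is coded as exposed. On the assumption that antibodies take longer than the stay to appear, that procedure cannot have caused the antibody measured. Reading the items as lifetime-ever does not help, because a lifetime includes the present stay.

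What is at stake is the surgery and hemodialysis rows of the exploratory risk-factor analysis. No adjustment is planned, so the coding of exposure feeds directly into the test. A second, separate problem is that the form asks a different question from the one Table 1 defines for the residual surgery class.

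**Working it through.** **The plan's own figure.** Section 5.8 gives 1,151 per institution. With N = 280,186, p = 0.5, d = 0.05, z = 1.96 and design effect 3:

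n = 3 × 280,186 × 0.25 / [(0.05²/1.96²) × 280,185 + 0.25] = 210,139.5 / 182.59 = 1,150.9, rounded up to 1,151.

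It reproduces. Neither surgery nor hemodialysis enters it, so it stands.

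**Can same-stay procedures be removed at analysis?** That would need one of three things:

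- Procedure date: absent from Table 1 and Annex 1.
- Admission date: absent from both.
- Recruiting service (ward, emergency, outpatient), for a sensitivity analysis in outpatients: absent; only the institution is recorded.

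So the answer is no, from the data the study collects.

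**Size of the dilution for surgery.** All inputs here are assumptions, because the documents give none of them. Let e be the share with earlier surgery, f the share of the rest operated on in the current stay before the form, and RR the true risk ratio for earlier surgery. Suppose same-stay patients have the same antibody risk as the never-operated. Then

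observed ratio = [e × RR + (1 − e) × f] / [e + (1 − e) × f].

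With RR = 2:

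| e | f | Calculation | Observed |
|---|---|---|---|
| 20% | 20% | 0.56 / 0.36 | 1.56 |
| 30% | 10% | 0.67 / 0.37 | 1.81 |
| 20% | 5% | 0.44 / 0.24 | 1.83 |
| 50% | 5% | 1.025 / 0.525 | 1.95 |
| 30% | 2% | 0.614 / 0.314 | 1.96 |
| 50% | 2% | 1.01 / 0.51 | 1.98 |

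The first and last rows are the extremes for e of 20-50% and f of 2-20%.

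**Effect on the test.** Assume 1,151 participants, 2% antibody prevalence in the unexposed and a true odds ratio of 3, with a two-sided 5% normal-approximation test and no allowance for clustering. Power is given in brackets.

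| Earlier exposure | f = 0 | f = 5% | f = 10% | f = 20% |
|---|---|---|---|---|
| 10% | 3.00 (65%) | 2.36 (52%) | 2.03 (43%) | 1.70 (29%) |
| 30% | 3.00 (88%) | 2.78 (84%) | 2.61 (80%) | 2.35 (69%) |

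**Direction.** If same-stay patients have k times the baseline risk for other reasons, the second term of the numerator becomes (1 − e) × f × k. With e = f = 20%, RR = 2 and an assumed k = 3, the observed ratio is (0.40 + 0.48) / 0.36 = 2.44, which is above the true 2. Dilution is therefore conditional on k being near 1.

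**Threshold, side by side.** For the residual surgery item:

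- Table 1, conceptual column: surgery "that may require post-procedural in-hospital monitoring".
- Table 1, operational column: more than 24 hours of surveillance.
- Annex 1: any surveillance, with no duration.

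A Yes on the form includes stays of 24 hours or less, which the operational definition leaves out, and no other field separates them.

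**The case against.** The strongest objection is that little depends on this. The study is descriptive. Its general objective is prevalence, which is not computed from either variable, and section 5.10 plans chi-square tests without naming a ratio as an estimate. This stands: it confines the point to an exploratory objective. It does not remove the point, since the same coding determines the table that is tested.

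Next, the effect may be negligible. The surgery definition is broad and everyone over 50 is eligible, so earlier surgery may be common, and outpatients dilute the same-stay share. This also stands, and the upper end of the range (1.95 to 1.98) reflects it.

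The direction is not assured either, least of all for dialysis. Section 5.3 itself lists chronic renal failure among conditions potentially associated with the infection. That makes the bias unpredictable rather than absent.

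The threshold mismatch concerns one sub-item of four, and the form is no wider than the conceptual column of Table 1. That is true, but Table 1 then differs between its own columns, and the operational column is the one that defines the coded variable.

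Could dates be recovered from hospital records through the identification number? The plan provides no such step, and Annex 2 restricts that number to linking the rapid test with the viral load.

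A reader might infer more than the documents support:

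- That same-stay procedures make up much of the exposed group. No share of inpatients, surgical patients or new dialysis starts is given.
- That the antibody is found days after the procedure. No interval from procedure to test is stated, and screening may come first.
- That a false difference between hospitals results. Section 5.10 specifies no comparison of surgery effects by hospital, and recoding an exposure cannot change antibody prevalence in any hospital.

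**Conclusion.** The point holds in a limited form. Surgery and hemodialysis have no time anchor, current inpatients are eligible, and the collected data cannot separate same-stay from earlier procedures. Same-stay procedures therefore enter the section 5.10 tests as exposure.

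The size is unknown. Under the assumed shares, and if same-stay procedures are unrelated to antibody status, a true risk ratio of 2 for surgery appears as about 1.56 to 1.98, which runs from material to trivial. If they are related, the direction is open. These ratios were worked for surgery; for hemodialysis the gap in definition is the same, but no plausible shares are available.

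The threshold discrepancy needs no assumption: Annex 1 cannot produce the residual surgery variable that Table 1 defines.

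A reader might also conclude that the prevalence estimate or the sample size is compromised. Neither is calculated from these variables. Hemodialysis is an eligibility factor under 50 ("Anyone who has undergone hemodialysis", section 5.3) and is undated there too, but that governs who is screened and not how prevalence is computed.

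This is worth correcting before data collection because the information is lost if it is not asked for, and asking costs almost nothing.

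**What to change.** - In Table 1 and Annex 1, word the surgery and hemodialysis items as *before the current admission or visit*, Yes/No.
- In section 5.10, state that only those earlier procedures count as exposure.
- Reconcile the surveillance threshold, so that both columns of Table 1 and Annex 1 give the same one.

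A year field is optional and not needed: a year cannot separate procedures within the same calendar year, whereas the wording can.

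The cost is slightly longer item text and minor recall error, with no extra visit, test or participant. Two limits remain. A procedure shortly before an outpatient visit or readmission still counts as earlier. Same-stay patients also move to the unexposed group, so if their risk differs for other reasons, ordinary confounding is still present.

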4.2 Specific objectives

- Characterize the study population socio-demographically.
- Describe the epidemiological characteristics of HCV antibody-positive patients.

- Determine the proportion of patients with positive HCV antibodies and positive viral load (quantitative) for HCV.
- Perform an exploratory analysis of the association of positive cases and the different risk factors for HCV infection.
- Quantify how many HCV-positive individuals were able to access the management pathway and treatment.

5 Methodology

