5.10 Data Analysis Plan

Descriptive analysis will be performed for all variables of interest proposed in this study. Descriptive statistics (frequencies and percentages) will be estimated. For continuous quantitative variables, measures of central tendency (mean and median) and measures of dispersion (variance, standard deviation) will be estimated. Possible relationships between sociodemographic variables, risk factors, and documentation of positive HCV antibodies will be explored, for which a bivariate analysis will be performed using X² (chi-square) tests to explore the proposed associations. All analyses will be performed with Stata version 18.

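### The exposure in section 5.5 covers tattoos, piercing and scarification, but the Annex 1 form has two overlapping fields and no scarification item, so the variable cannot be built as defined

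*Combined protocol and SAP*

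**What the plan says.** Four places bear on this exposure.

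- **Section 5.3 (Inclusion criteria)** lists "Persons who have had tattoos, body piercings, or scarification procedures" as one of the risk factors that make an adult under 50 eligible.
- **Section 5.5 (Table 1, Risk Factors)** names the variable "People who have had tattoos, body piercings, scarification, etc", so the name is open-ended. It defines the variable as "Presence of tattoos or piercing or scarification", coded 0/1.
- **Annex 1 (section 12.1)** carries two fields: "Tattoos: Yes ___ No" and, separately, "Have you ever had tattoos or body piercings? Yes ___ No". Neither mentions scarification.
- **Section 5.10** says that "a bivariate analysis will be performed using X² (chi-square) tests to explore the proposed associations". It does not list the variables to be tested. This serves the specific objective in 4.2: "Perform an exploratory analysis of the association of positive cases and the different risk factors for HCV infection".

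Section 5.9 provides for weekly review and validation of the captured data. It names no check between fields.

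**The concern.** The form and the variable table do not describe the same exposure. Eligibility and the variable definition both include scarification, and the form never asks about it. The tattoo field has no home in the variable table, and nothing says which of the two fields supplies the composite. An analyst would have to improvise, and different analysts could code the same form differently.

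There is also a question of interpretation. The table in 5.5 is the only list of risk factors in the plan, so testing the composite is the natural reading of 5.10. If the three procedures differ in their association with HCV antibodies, one Yes/No variable hides that, although the stated objective is to look at the different risk factors. At stake is how readable one row of an exploratory table will be; the main prevalence result does not depend on it.

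**Working it through.** **1. Is there a figure in the plan to reproduce?** None for this exposure. The sample size in 5.8 is the nearest: n = DEFF·N·p(1−p) / [(d²/z²)(N−1) + p(1−p)] with DEFF 3, N 280,186, p 0.5, d 0.05 and z 1.96. This gives 1,150.9, against 1,151 stated. It reproduces, and it does not involve this variable.

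**2. What each place covers.**

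| Place | Tattoo | Piercing | Scarification |
|---|---|---|---|
| 5.3 eligibility item | yes | yes | yes |
| 5.5 definition | yes | yes | yes |
| Annex 1, tattoo field | yes | no | no |
| Annex 1, combined field | yes | yes | no |

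Someone with scarification only is Yes under 5.3 and 5.5 and No on both form fields. If such people make up a share q of those recorded as unexposed, and their risk ratio is R, a true ratio of R is observed as R / [1 + q(R − 1)]. The documents do not give q, so this error has a direction (towards 1) but no size.

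**3. What the two fields can tell an analyst.**

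| Tattoos | Tattoos or piercings | Meaning |
|---|---|---|
| Yes | Yes | tattooed; piercing unknown |
| No | Yes | piercing only |
| No | No | neither; scarification unknown |
| Yes | No | contradictory |

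Consistent answers therefore allow a tattoo variable and a piercing-only variable. They do not show piercing among the tattooed, and they never show scarification.

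**4. Attenuation if only the composite is tested and piercing has no effect.** Assumptions, none from the documents: share tattooed t = 0.20; share pierced p = 0.30 or 0.50, independent of tattooing. Exposed share s = 1 − (1 − t)(1 − p). Observed ratio against the never-exposed = [tR + (s − t)] / s.

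- p = 0.30: s = 1 − 0.8 × 0.7 = 0.44. R = 2 gives (0.40 + 0.24)/0.44 = 1.45; R = 3 gives (0.60 + 0.24)/0.44 = 1.91.
- p = 0.50: s = 1 − 0.8 × 0.5 = 0.60. R = 2 gives (0.40 + 0.40)/0.60 = 1.33; R = 3 gives (0.60 + 0.40)/0.60 = 1.67.

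**5. The assumption that decides it: the piercing effect.** Take 10% tattooed, 20% pierced only, 1% positive among those with neither, and 7 × 1,151 = 8,057 people; all but the 1,151 and the seven institutions are assumed. An odds ratio of 2 puts the tattooed at 1.98%. Power is for a two-sided 5% test of two proportions: Φ[(|p₁ − p₂| − 1.96·SE₀)/SE₁], with SE₀ pooled and SE₁ unpooled. The design effect of 3 is not applied, so all powers are optimistic.

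| Piercing effect | Comparison | Odds ratio | Power |
|---|---|---|---|
| none | composite v neither | 1.33 | 0.26 |
| none | tattoo v no tattoo | 2.00 | 0.67 |
| same as tattoo | composite v neither | 2.00 | 0.92 |
| same as tattoo | tattoo v everyone else | 1.64 | 0.45 |
| either | tattoo v neither | 2.00 | 0.65 |

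For the first row, the composite risk is (0.10 × 1.98% + 0.20 × 1%)/0.30 = 1.33%, an odds ratio of 1.33. For the fourth, the reference risk is (0.20 × 1.98% + 0.70 × 1%)/0.90 = 1.22%, an odds ratio of 1.64. In the last row the reference group contains no pierced people, so the piercing effect does not enter.

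**The case against.** The best defence is that the composite follows the eligibility item in 5.3, the association analysis is declared exploratory, and the form already holds a tattoo field from which a tattoo-only analysis can be made. Contradictory answers are ordinary data cleaning, and 5.9 and Annex 2 both provide for validation of incoming data. Splitting the variable also costs power if the procedures carry similar risk.

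Most of this stands as a limit on the point. Grouping the procedures is defensible, and section 5.10 does not rule out testing tattoo alone. But the defence does not reach scarification, which no field records. Nor does it supply a rule for the contradictory pair or say which field feeds the variable.

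A reader might go further and infer that common piercings, ear piercing included, must dilute any tattoo effect to almost nothing and turn the composite into a marker of sex. The documents do not support that. They give no frequency of tattoos or piercings, overall or by sex, and no effect sizes. The eligibility item, the variable name and the form all speak of body piercings; only the definition says piercing without qualification. Even with no piercing effect, the ratios in step 4 are attenuated but not close to 1.

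**Conclusion.** The mismatch between form and variable table holds on the text alone. The exposure defined in 5.5 cannot be fully built from Annex 1, scarification-only exposure is recorded as none, and one answer pair in four is contradictory without a rule.

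The attenuation holds only conditionally. It requires that the composite alone is tested and that piercing has a weaker association than tattooing. Under the stated assumptions with no piercing effect, a ratio of 2 appears as 1.45-1.33 and a ratio of 3 as 1.91-1.67. With equal effects there is no attenuation and the composite has the greater power. Since the documents do not say which case applies, the data should be able to show it.

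The point is minor: one row of an exploratory analysis, with no effect on the prevalence estimate or the sample size.

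**What to change.** - **Annex 1:** replace the two overlapping fields with three Yes/No fields: tattoo, body piercing, scarification. This removes the contradictory pair and leaves eligibility as it is.
- **Section 5.5:** give each field its own row, and define the composite as Yes if any of the three is Yes. Drop the open ending from the variable name so that it matches what is collected.
- **Section 5.10:** state that each component is compared with people who have none of the three, and reported beside the composite, all as exploratory. That reference group keeps pierced people out of the comparison for tattoo.
- **Forms already completed, if any:** query the contradictory pair, derive tattoo and piercing-only from the consistent pairs, and treat scarification as not recorded, not as No.

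The cost is a small form edit, extra rows in one table, fewer exposed people per row and a few more exploratory tests. Keeping the composite preserves its power should the three procedures prove similar.
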